### 15. Withdrawal of Subjects

Participants may withdraw from the study at any time without penalty. To protect the integrity of the research study, data collected up to the time of subject withdrawal will remain in the database and managed according to the protocols outlined in Section 16. Alternatively, subjects may submit written notification that they intend to withdraw their authorization for their data to be used in the current study, which is described to participants in the detailed consent statement.

### 16. Data Management/Confidentiality

- All data are coded with a unique research subject identifier (URSI) number. Electronic data is stored on password protected computers only accessible by the research team, and on the COINS database on a secure HIPAA compliant cloud-based server. For non-computer based forms, the data collection sheets are stored in a locked cabinet in a locked office.
- Paperwork with identifying information—namely, payment receipts and study consent forms—will be stored in a locked filing cabinet in the CBRR while the study is being conducted, and retained there for long-term storage after data collection is complete. The laboratory's door will be kept locked, and located within the Psychology Clinical Neurosciences Center (PCNC) on the second floor of Logan Hall, which is only accessible to approved PCNC staff. These forms will be maintained for a maximum of 7 years after which they will be shredded by a member of the research team.
- Additionally, the CBRR maintains a repository of documents on REDCap (Research Electronic Data Capture) to trace subjects and their documents for use during audits, or for the potential future benefit of the participant. The Research Supervisor and two research staff will have access to this repository. MRN also retains the link between identifiers and URSI indefinitely for the potential future benefit to the research participant. For example, it may become medically advantageous in the future for a former participant to have access to the clinical information that is present in most radiological scans. For example, if a participant is diagnosed with a neurological condition (e.g. multiple sclerosis, glioblastoma, TBI, etc.) it may be clinically beneficial for the participant's physician to have access to a research scan that was performed at an earlier time-point to determine disease course and severity. Both the Phone Screen spreadsheet and Master Key spreadsheet are password

## NONINVASIVELY MODULATING MOTIVATIONAL BRAIN REGIONS

protected and only accessed by the Research Coordinator as per UNM North Campus IRB suggestions.

- All assessments will be administered electronically and tracked using the participant's URSI number, and no personally identifiable information. During data collection and analysis, all electronic data will be stored on COINS, on servers at the Center for Advanced Research Computing (CARC) for advanced fMRI data processing pipelines, and accessed using secured computers in either the PI's office or laboratory at Logan Hall on main campus. The data will be archived via local backups to secured servers maintained by PCNC staff.
  - In order to further protect the confidentiality of participant data, NIH-funded projects automatically fall under a Certificate of Confidentiality (CoC). With this certificate, the investigators cannot be forced (for example, by court subpoena) to disclose research information that may identify the participant in any Federal, State, or local civil, criminal, administrative, legislative, or other proceedings. Disclosure will be necessary, however, upon request of DHHS or other federal agencies for audit or program evaluation purposes. The CoC will not prevent the participant or a member of the participant's family from voluntarily releasing information about themselves or their involvement in this research. Note however, that if an insurer or employer learns about the participant's participation, and obtains consent to receive research information, then the investigator may not use the CoC to withhold this information. This means that the participant and the participant's family must also actively protect their own privacy and the confidentiality of their data. Finally, the investigator is not prevented from taking steps, including reporting to authorities, to prevent serious harm of the participant or others.

## 17. Data and Specimen Banking

To promote open and rigorous science practices, de-identified behavioral data and skull-stripped MRI data (i.e. with any potentially identifiable facial features removed from the brain images) will be hosted for use by external researchers through the COINS Data Exchange System. The data storage and sharing plan is described in the informed consent statement.

Additionally, Participants will be given the option of having their data stored in the MRN Data Repository (see HRRC# 06-387, PI: [name]).

## 18. Risks to Subjects

- Contrast-free MRI has not been associated with any known adverse effects and is considered minimal risk by the FDA and OHRP.

## NONINVASIVELY MODULATING MOTIVATIONAL BRAIN REGIONS

- Since the scanner is a powerful magnet, it is possible to move objects containing ferrous metal in the room during the scan. Accordingly, as per MRN policy, all participants will wear MRI-compatible scrubs for the scan, and will complete a safety screening form to reveal any contraindications to MRI (**Appendix 3**) prior to completing study protocols.
- On rare occasions, some participants may experience discomfort due to claustrophobia when inside the MRI scanner. For such events, an emergency squeeze ball will be provided to participants. This ball elicits an alarm in the MRI control room, which will enable the MRI technologist/research team to rapidly extricate participants from the scanner if needed.
- The scanner produces loud ‘drum’ beating noises that are slightly different across the different scanning protocols. During the consent process, each of these different scanner noises will be played for the participant via headphones, to ensure they are familiar with these sounds prior to entering the scanner environment. Additionally, noise attenuating headphones will be provided for ear protection during the MRI protocols.
- On rare occasions, large or recent tattoos can heat up during an MRI scan and cause skin irritation like a sunburn. All recent tattoos will be cleared with the MRI technician before scan sessions to reduce burn risk.
- The current protocol will follow HRRC-approved MRN MRI policy for pregnancy testing adult females (page 2 of **Appendix 26**). Specifically, all females who have had their first menstrual period must answer “no” to the question on the safety screening form that asks if there is any possibility of being pregnant. If there is any uncertainty, or if the participant requests to take a pregnancy test, a urine pregnancy test will be administered and documented as negative prior to MR imaging. Testing is the responsibility of the PI and/or their designated research team members. All results are confidential and are discussed with the participant alone (regardless of participant age) in compliance with applicable laws and regulations. In the event of an unexpected positive pregnancy test, participant partners, family members, and parents may be told that the participant is not eligible for MR scanning, but no further explanation is given unless requested by the participant.
- Due to the very high sensitivity of MRI in detecting abnormalities, there is a risk of false-positive findings. This may result in anxiety and additional testing, possibly including a recommendation for clinical scans at your cost. The radiology report or other study data will not be put into participant medical record unless they provide it to their physician. If the radiology report becomes part of their personal medical record, it may or may not have an effect on their getting health insurance or life insurance in the future.
- TMS is considered a minimal risk procedure but can produce side effects that are noted here. Most people do not find TMS painful but occasionally strong

## NONINVASIVELY MODULATING MOTIVATIONAL BRAIN REGIONS

contractions of the scalp muscles can cause discomfort or headache that usually go away promptly with nonprescription medication. The noise of the TMS magnet may affect hearing, so participants will be fitted with earplugs. Like MRI, TMS involves the use of a powerful magnet. Thus TMS will not be performed on people who have pacemakers, implanted pumps or stimulators, or who have metal objects inside their heads. The risk of inducing seizure with rTMS is considered very low at <0.1%. However, certain factors increase the risk of seizure such as sleep deprivation, family history of seizures, polypharmacy, alcohol use, and previous neurological conditions. Participants will be carefully screened for these factors to ensure that risk of seizure is minimized (**Appendix 4**).

- The CBRR and MRN are both located on the UNM North Campus, in close proximity to the UNM-ER. Therefore, participants will have rapid access to an emergency facility should an unforeseen medical emergency occur during testing.
- Participants will be told that they will only win a \$20 merchandise card on the primary task of interest (Bandit task) if they perform it well. However, at the end of the task all participants will receive the same compensation regardless of task performance. This protocol is used to ensure high motivation to perform the Bandit task, but may lead some participants to feel deceived at the end of the study. Accordingly, the reason for this procedure—i.e. “to ensure participants are motivated to try their best on the Bandit task”—will be explained clearly during a debrief at the end of the experimental session.
- During the SARS-CoV-2 pandemic, the current study’s procedures will be in accordance with the guidelines provided by the State of New Mexico and UNM-HSC Office of Research for maintaining physical distancing and face coverage. While supporting the efforts to reduce the spread and risk of infection, COVID-19 exposure is a potential risk associated with this study.

### 19. Potential Benefits to Subjects

- Participants will help science and medicine better understand how TBI impacts the brain and decision-making and may help to better diagnose psychiatric problems in TBI patients using brain imaging.

### 20. Recruitment Methods

HC participants from the community will have been recruited via a flier that will be posted in public buildings, local businesses, and through other advertisement mechanisms such as the Weekly Alibi local newspaper, Craigslist, etc. From the participants’ perspective, all study advertisements will appear as either the study flier (**Appendix 5**), or one of the approved online advertisements (**Appendices 6-7**). Electronic links to the study flier will appear as an approved link phrase (Appendix 29) and the approved thumbnail (Appendix 30). In certain instances, targeted advertisement through social media platforms (Facebook, Instagram, or Twitter) may be

## NONINVASIVELY MODULATING MOTIVATIONAL BRAIN REGIONS

used to ensure a demographic match between the current study and linked clinical study 19-053. In particular, if the current sample and 19-053 are unmatched with respect to age or sex, we will use widely-available advertisement filtering algorithms on these platforms to ensure that individuals from particular age or sex groups in the local Albuquerque community are more likely to see our approved recruitment materials. This step will be critical from a scientific perspective, ensuring our final sample will enable a valid comparison between our key outcome measures between the current study and 19-053. HC participants who consented to be contacted for future studies within the COINS system may also be contacted within the current protocol.

## 21. Provisions to Protect the Privacy Interests of Subjects

- Participants will be assigned a unique research subject identifier (URSI) number prior to their arrival on the day of their study participation, which will link their data with their name and other identifying information in the COINS system. After data collection is complete, the linking code will be made inaccessible to the research team.
- Participant behavioral testing rooms at the CBRR are equipped with white noise generators to ensure privacy during testing.
- The MRN has private changing rooms including lockers for participants to store their personal items during the MRI portion of the protocol.

## 22. Economic Burden to Subjects

Participants will not be charged for any of the experimental study procedures, including MRI scans and TMS sessions. If incidental findings from the study result in the need for further evaluation/treatment, the participant or their insurance company will be responsible for additional clinical evaluation/treatment that may be needed. Also, incidental finding information is disclosed only to the individual participant. However, if a participant chooses to disclose such information also to their personal physician, this may become part of their medical record which may or may not have an effect in the future on getting health or life insurance.

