## NONINVASIVELY MODULATING MOTIVATIONAL BRAIN REGIONS

- The protocol will recruit male and female adults (18-55 years old) of any ethnic background. All recruited participants will be capable of providing informed consent.
- Participants will have 12 or more years of education and the ability to provide informed consent independently.
- Exclusion criteria will be: any condition that would prevent the subject from being able to complete the protocol, prior history of neurological disease or any history of seizures (including prior history of TBI; i.e., any loss of consciousness  $\geq 1$  minute), not fluent in English, any contraindications to MRI or TMS (**Appendices 3-4**), history of substance abuse (excluding moderate alcohol or marijuana usage), a medical diagnosis of psychosis or mania, or stable doses of antipsychotics or mood stabilizers taken for less than two months.
- Participants who are found to have falsely represented any factors which should exclude them from the study, or who are unable to follow the study protocols for study session attendance may be withdrawn prematurely from the study.
- To reduce the possible spread of COVID-19, during the SARS-CoV-2 pandemic any participants who answer “yes” to any of the items in Question 34 of the Phone Screen (**Appendix 1**) will be excluded from the study at this time.

*4.3. Indicate specifically whether you will include each of the following special populations: (You may not include members of the above populations as subjects in your research unless you indicate this in your inclusion criteria.)*

The study will not recruit from the following special populations: adults unable to consent, individuals who are not yet adults, pregnant women, or prisoners.

*4.4. Indicate if you excluding any particular populations (e.g., women, children, persons not fluent in English, a particular racial or ethnic group, etc.) and provide justification.*

Individuals not fluent in English will have difficulty performing the behavioral assays used in the current protocol, and will find it difficult to understand the study protocols to the point where they are capable of providing truly informed consent. Accordingly, proficiency in the English language is a requirement for the current protocol.

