## **6. Study Timelines**

### *6.1. Describe:*

Participants recruited for the study will be invited to complete three experimental sessions as soon as it is convenient for them to come in. The three experimental sessions will include one MRI scan (1-2 hours per scan). The first session will include all questionnaires and assessments (maximum time: 170 minutes, see Table 1). The second and third sessions will include rTMS administration including motor thresholding ( $\approx 20-40$  minutes), neuronavigation ( $\approx 10-20$  minutes) and rTMS delivery ( $\approx 3-20$  minutes, depending on the specific pulse sequence). The total rTMS session will last  $\approx 1-1.5$  hours, and will be immediately followed by an MRI scan (total session time: 3-4 hours for day 1, 4-5 hours for day 2). It is expected that data collection targets will be reached by September, 2022.

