## 12. Study Procedures

The study will be conducted in three 3-6 hour sessions which can be arranged to accommodate participants' schedules. The three sessions will take place with no less than 24 hours, and no more than two weeks apart between each study visit. Approximately 24 hours prior to the scheduled date, the participants will receive an email and a phone call including important information for them to be aware of prior to coming in for the study (**Appendix 9**). An IRB-approved member of the research team will greet participants, and will go through the study consent procedures.

SARS-CoV-2 related note: For the duration of the SARS-CoV-2 pandemic, consent procedures will be completed remotely via a HIPAA-compliant Zoom account or phone call, with participants receiving the document via email. They will then sign the consent document when they appear in person for their study visit. A note to file will be created for each consent signed in this way.

Additionally, for the duration of the visit the participant and experimenter will remain physically-distanced as much as possible, will both be wearing face coverings, and the experimenter will also be wearing a laboratory coat to reduce the risk of SARS-CoV-2 spread through droplets. During the TMS protocol, an acrylic divider will be used whenever possible to separate the participant and experimenter. MRI scans will be completed using HRRC approved protocols for scanning during the SARS-CoV-2 pandemic.

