## NONINVASIVELY MODULATING MOTIVATIONAL BRAIN REGIONS

handheld TMS coil (Magventure MagPro; Magventure, Inc., Alpharetta, Georgia, USA). TMS pulses will be delivered through an air-cooled coil in either a figure-eight or double-cone shape, with the latter being particularly useful for targeting deeper structures such as dACC. The first phase of the TMS protocol will involve a standardized motor-thresholding procedure, wherein peripheral responses evoked by single TMS pulses are recorded via an electromyographic recording device (BioPac psychophysiological recording system; BIOPAC Systems, Inc., Goleta, CA). In this phase, the TMS coil's stimulation intensity is titrated to a level that is comfortable yet effective at reliably exciting neuronal populations orthogonal to the coil (50% MEPs  $\geq 50\mu\text{V}$ ; typical duration  $\approx 20\text{-}40$  mins). Then, the repetitive TMS (rTMS) procedure will be administered to a pre-determined cortical target based on the individual's pre-TMS fMRI scan using a Localite Neuronavigation system (TMS Navigator, Localite GmbH, Bonn, Germany; duration  $\approx 10\text{-}20$  mins). The rTMS protocol will involve the delivery of a train of TMS pulses over a cortical target prior to performance of the behavioral tasks during a post-rTMS fMRI scan.

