**27. Study Test Results/Incidental Findings**

- MRI Reading: All research MRI scans are read for incidental findings by a radiologist. When the scan is read, an e-mail notification is sent to the participant letting them know new results are available. The participant can securely log in to the COINS Homepage to access their MRI radiology report. No sensitive or identifying information is sent via e-mail. If an abnormality that requires follow-up is identified, such as a Doctor Referral recommendation, a hard copy of the report may be mailed to the participant in addition to the e-mail notification. In these cases, the MRN Medical Director may also attempt to contact the participant by phone to explain the information and help answer questions.

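### The session-1 MRI read has no deadline and no written route to the study team before rTMS, so a newly found exclusion reaches them only if the participant reports it or someone acts outside the plan

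*Combined protocol and SAP*

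**What the plan says.** **Scan before stimulation.** Section 6.1 states: "The three experimental sessions will include one MRI scan (1-2 hours per scan". It adds: "The second and third sessions will include rTMS administration including motor thresholding". Section 12 (TMS Protocol) directs rTMS to a "pre-determined cortical target based on the individual's pre-TMS fMRI scan". The session-1 scan therefore precedes all rTMS and is used by the team for targeting.

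**Read and reporting.** Sections 9.2 and 27 have a radiologist read all research scans. Section 27 says: "When the scan is read, an e-mail notification is sent to the participant letting them know new results are available". The participant logs in to COINS to see the report. If follow-up is needed, a paper copy may be mailed and the MRN Medical Director may try to phone, in both cases to the participant. Section 22 states that "incidental finding information is disclosed only to the individual participant".

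**Timing.** Section 12: "The three sessions will take place with no less than 24 hours, and no more than two weeks apart between each study visit".

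**Eligibility and risk.** Section 4.2 excludes "prior history of neurological disease or any history of seizures", together with TMS contraindications. Section 18 lists earlier neurological conditions among the factors that raise seizure risk, to be screened through Appendix 4, which section 12 describes as a questionnaire. Section 14 names moderate-to-severe TBI, multiple sclerosis and stroke as risk factors.

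**Withdrawal by the investigator.** Section 4.2 mentions "Participants who are found to have falsely represented any factors which should exclude them from the study" and people who cannot follow the attendance requirements.

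**The concern.** The trial already obtains and reads a brain scan on each volunteer before the first stimulation session. The eligibility and seizure-risk screening described in the plan relies on self-report, which cannot reveal a condition that the participant does not know about. The read could. Yet the plan gives it no due date and no recipient on the study side.

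Two things are at stake. The first is safety: information bearing on the trial's own exclusion criteria may exist and not be in front of the people who deliver rTMS. The second is interpretation. A lesion could affect the individual target and the activation and connectivity measures in aim iii of section 1.1. If it becomes known after sessions 2 and 3, no rule says when, or with what knowledge of the outcomes, the team decides whether that person counts toward the 42 completers in section 7.1.

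**Working it through.** The plan states no figure on this point, so the check is a trace through the sections, followed by simple timing arithmetic.

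**Trace**

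1. *Is there a scan before rTMS?* Yes. Section 12 is uneven on the number of MRI sessions (two sessions, but on three days). A session-1 scan follows on either count, because the target depends on a pre-TMS scan and the resting-state and task runs are repeated after rTMS at sessions 2 and 3.
2. *Is it read?* Yes, by a radiologist (sections 9.2 and 27).
3. *By when?* Not stated.
4. *Who is told?* The participant (sections 22 and 27). The MRN Medical Director may know of a finding that needs follow-up, but the only contact described is an optional call to the participant.
5. *Is the investigator, the rTMS operator or the DSMB told?* No section says so.
6. *Is the read linked to session 2?* No section links them.
7. *Is an exclusion found after enrolment addressed?* Not explicitly. The two withdrawal grounds in section 4.2 do not describe a participant who honestly did not know of a condition.

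**Comparison within the plan.** Section 9.2 also covers the suicidality item of the Beck Depression Inventory. That item is examined within 24 hours and the investigator is notified at once. The MRI read, in the same section, has neither a time limit nor a recipient. Section 14 has the DSMB ask, after a seizure, whether risk factors were missed in consent and contraindication screening. The MRI read is not named there either.

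**Timing.** Let R be the days from scan to finished report (not given in the plan) and G the days from session 1 to session 2. The report arrives too late for session 2 if R > G. From section 12, G runs from 1 to 14 days:

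- shortest spacing: too late if R > 1 day;
- longest spacing: too late if R > 14 days.

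Even when R is below G, the written route ends with the participant.

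**Weight of one case in the analysis.** One affected person is 1/42 = 2.4% of the final sample. Section 12 also plans a look at behavioural and connectivity data after 10 participants, where one person is 1/10 = 10%. Because outcomes are viewed during the trial, the order of eligibility decision and outcome viewing matters before the end of the study.

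**Why no probability is offered.** The documents give no rate of eligibility-relevant findings. For an assumed rate p, the chance of at least one among 42 is 1 − (1 − p)^42:

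| Assumed p | Chance of at least one |
|---|---|
| 0.1% | 1 − 0.999^42 = 4% |
| 1% | 1 − 0.99^42 = 34% |
| 3% | 1 − 0.97^42 = 72% |

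The assumption alone moves the answer from 4% to 72%. None of these figures supports the point, and the point does not need them.

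**The case against.** A reader might infer that a finding cannot stop stimulation, or that the team would knowingly stimulate an excluded person. The documents do not support that. The participant receives the report, can tell the team, and may withdraw at any time (section 15). The Medical Director may phone. The 24 hours is a minimum. Nothing forbids the team from acting on an exclusion once it is known.

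Other parts of the opposing case also have force:

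- **Section 22 is about cost, medical records and insurance.** Its sentence may be meant as reassurance about outside disclosure rather than as a bar on the study team. That is a fair reading of intent. The wording is nevertheless unqualified, and section 27 supplies no other recipient.
- **The withdrawal grounds are not exhaustive.** Section 4.2 says that such participants may be withdrawn, not that only they may be. Its criteria define the final sample and so still apply to an exclusion found later. What remains is that no timing or procedure is given for that case.
- **The team handles the images itself,** for quality control (section 13.1) and targeting (section 12), and COINS holds both the reports and study data. The plan does not describe this handling as a clinical read, and it does not say whether staff can see the reports.
- **An incidental finding is not automatically a history of neurological disease,** and section 18 warns of false positives. That is a reason to have a responsible clinician judge a finding. It does not explain why the result has no route to one on the study side.
- **Appendix 4 and the consent form are not in the text.** A repeat screen on the rTMS day or a disclosure clause cannot be ruled out.

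**Conclusion.** The concern holds in a limited form. The plan sets no deadline for the session-1 read and describes no route from it to the study team before rTMS. A newly found condition bearing on the exclusions and seizure-risk factors in sections 4.2, 14 and 18 therefore reaches the team in time only through the participant or through action outside the written plan. This is more than a missing detail, because section 22 states a disclosure rule which, followed literally, keeps the result from the team.

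The gap covers all 42 participants, with 1 to 14 days available for the read. How often it would matter is unknown. The conclusion assumes that the consent form and appendices contain no such route. With the participant's own route open and no rate available, the point ranks below must-fix: it should be corrected, at little cost.

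**What to change.** Reconcile sections 22 and 27 with sections 4.2, 12, 14 and 18:

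1. State that an eligibility-relevant result from the existing session-1 read, or a yes/no flag for one, also goes to a named study-side role, and amend section 22 to match.
2. State when that result or flag is due relative to session 2.
3. Add a matching sentence to the consent form.
4. State that eligibility decisions on exclusions found after enrolment are made and recorded before that participant's outcome data are viewed, including at the look after 10 participants.

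What any finding means for stimulation stays with the responsible clinician, and no clinical rule is proposed here.

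The cost is a consent sentence, a scheduling check, a limited disclosure to the study team and possibly a short delay to session 2. Whether that delay fits the two-week limit depends on the read time, which the sponsor should state. No additional scan or reader is needed.
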